11.3. Analysis populations

The per protocol (PP) population will include all patients who received their allocated treatment and did not have any major protocol deviations with available data at all time-points up to and including 12 months. Major protocol deviations will be pre-specified in the Data Management Plan and SHEAP and finalised following a blinded review of the data prior to the primary outcome analysis data-lock.

The Intention-to-Treat (ITT) population will include all participants with available data at all time-points up to and including 12 months in the randomised groups to which they were allocated regardless of which treatment they actually received.

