11. STATISTICS AND ANALYSIS

All available data from both treatment arms will be used in data analysis. Reporting of the results will be in accordance with the CONSORT statement ³¹ using the extensions for non-pharmacological treatment interventions and patient-reported outcomes. Baseline demographic data will be summarised to check comparability between treatment arms. Standard statistical summaries and graphical plots will be presented for the primary outcome measure and all secondary outcome measures. Differences between treatment groups will be assessed on both an intention-to-treat and per protocol basis, using a normal approximation for the OMAS score, ²¹ at four months post-treatment, and at additional time-points.

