11.2. Sample Size Determination

The primary clinical outcome is OMAS at 4 months. Previous studies have demonstrated a minimally clinical important difference (MCID) of 10 points, ^{3 32} which is in accordance with expert opinion (for scales scoring 0-100) and statistical convention. ^{3 33} We have selected a standard deviation (SD) of 21.8 based on the largest published RCT studying the OMAS within six months of surgically treated ankle fracture. ³ Although AIM included participants aged over 60 years we are not expecting the variability in OMAS in participants aged 60 years and younger to be different. A non-inferiority margin of 5 points has been chosen. This is half the MCID (one method of choosing the non-inferiority margin) and this has been discussed with clinical experts who felt that this would provide enough evidence to change clinical practice, whereas using 6 points (as AIM used for its equivalence margin) would be less convincing in this patient population.

800 participants providing data at four months will provide 90% power and 2.5% (1-sided) significance to detect whether non-surgical treatment for the treatment of unstable ankle fractures is non-inferior to surgical treatment using a non-inferiority margin of -5 points on the OMAS score at four months. Allowing for 10% loss to follow-up, this yields an overall target of 890 participants (445 per arm). ³⁴ Essentially the lower 95% confidence interval of the treatment difference is assessed against the non-inferiority margin

of -5 points and if it lies above this then the trial will be assessed as non-inferior. If non-surgical management is found to be non-inferior to surgical management of unstable ankle fractures then superiority will also be tested at 2.5% (1-sided) significance (the equivalent of comparing the lower 95% confidence interval against Zero rather than -5 points).

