11.4. Description of the Statistical Methods

In non-inferiority trials we want to show that the new treatment is not clinically worse than the active control and therefore the interest is one-sided. The new treatment may be better than the control, but it is at least non-inferior to it. We define a non-inferiority margin (Δ_T), which is the maximum difference we are prepared to tolerate in a given direction that the new treatment is not to be considered clinically inferior to the well-established standard treatment. The null hypothesis is therefore that a difference of greater than Δ_T exists in favour of the standard treatment (H₀: $\Delta \le -\Delta_T$) (Δ defined as the difference between treatment and control (T-C)) and the trial is targeted at disproving this in favour of the alternative that the new treatment is non-inferior (H_A : $\Delta \ge -\Delta_T$). This will be assessed by creating a 95% confidence interval which should be entirely above the non-inferiority margin for the new treatment to be declared noninferior. FDA regulations recommend that both a treatment received (per protocol) and intention to treat (ITT) analysis is performed aiming to demonstrate non-inferiority. Use of the ITT approach as in a superiority trial sometimes increases the chance of falsely claiming non-inferiority. Therefore, the primary analysis will be undertaken on the per-protocol population, where only those patients who received their allocated treatment will be analysed and those that do not will be excluded from the analysis. A secondary analysis will be undertaken on the ITT population where all randomised patients will be analysed according to their treatment allocation.

The result of the analysis for the primary endpoint should be one of the following:

- The confidence interval for the difference between the two treatments lies entirely above the noninferiority margin (-ΔT), so that non-inferiority may be concluded with only a small probability of error.
- The confidence interval includes points below the non-inferiority margin, then there is a possibility that the new treatment is inferior to the control and non-inferiority cannot be safely concluded.
- The confidence interval is entirely above zero, indicative of a treatment effect, then superiority of the new treatment can be concluded within a small probability of error.

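### Section 11.3 makes data at every time-point to 12 months a condition of entry to both the PP and the ITT population, contradicting the four-month primary analysis and the rest of the protocol

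*Protocol*

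**What the plan says.** Protocol section 11.3 defines the two analysis populations. For ITT: "The Intention-to-Treat (ITT) population will include all participants with available data at all time-points up to and including 12 months", kept in their randomised groups whatever treatment they received. For PP, participants must have had their allocated treatment and must be people who "did not have any major protocol deviations with available data at all time-points up to and including 12 months". Section 9.9 sets the follow-up questionnaires in that period at 8 weeks, 4 months and 12 months.

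Other parts of the protocol describe the analysis set differently:

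- Section 11.2: "The primary clinical outcome is OMAS at 4 months", and "800 participants providing data at four months will provide 90% power".
- Section 11.4 describes the ITT analysis as one "where all randomised patients will be analysed according to their treatment allocation". It makes PP the primary analysis and ITT the supporting one.
- Section 11 opens with: "All available data from both treatment arms will be used in data analysis".
- Section 11.9 defends the primary method as reasonably robust when data are missing at random, on the ground that available data from every time-point are used.
- Section 9.11 keeps data collected before withdrawal because the ITT analysis needs them.
- Section 11.5 plans multiple imputation in both the PP and ITT analyses and says imputed primary-outcome estimates will be supplied to the statisticians.

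**The concern.** Population membership at a four-month endpoint should not depend on what a participant does eight months later. Section 11.3 makes it so. A person whose four-month OMAS is on the database, but who does not answer at 12 months, is outside both populations.

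Two things are at stake. The first is bias. Later non-response may relate to recovery and to treatment arm, and section 9.5 confirms that participants are unblinded; the outcome is self-reported. Dropping late non-responders can therefore shift the four-month difference in either direction. The usual safeguard in a non-inferiority trial is to set PP beside ITT, but both carry the same restriction, so agreement between them would say nothing about this bias. The second is information: observed primary outcomes would be discarded, and the number analysed could fall below the 800 on which power was calculated.

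**Working it through.** **1. Who is in and who is out.** Take four kinds of participant, all treated as allocated and without a major deviation.

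| Data present | PP and ITT under 11.3 | Counted in the 800 (11.2) | ITT under 11.4 |
|---|---|---|---|
| 8 weeks, 4 and 12 months | in | yes | in |
| 4 and 12 months only | out | yes | in |
| 8 weeks and 4 months only (including withdrawal after 4 months) | out | yes | in |
| 8 weeks and 12 months only | out | no | in |

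The second and third rows are the defect: the primary outcome is observed, the sample size relies on it, and section 11.3 removes it. The third row also conflicts with section 9.11. The fourth row is the case that the missing-at-random argument in 11.9 and the imputed primary-outcome estimates in 11.5 are meant to serve. Under 11.3 no member of either population lacks a four-month OMAS, so those estimates would be redundant.

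**2. Reproducing the stated sample size.** Inputs from section 11.2: "We have selected a standard deviation (SD) of 21.8"; "A non-inferiority margin of 5 points has been chosen"; 90% power; one-sided 2.5%; 10% loss. Section 9.4 gives 1:1 allocation. A true difference of 0 is not stated but reproduces the stated size.

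- Per arm: n = 2 × (1.960 + 1.2816)² × (21.8/5)² = 399.5, rounded up to 400, so 800 in total.
- Power at 400 per arm: Φ(5 / (21.8 × √(2/400)) − 1.960) = 90.0%.
- Inflation: 800/0.90 = 888.9, so 889, or 890 for equal arms.

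The plan's figures are right for participants with four-month data.

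**3. The same formula under the literal definition.** The protocol gives no rate for completion at all three time-points, so the rates below are assumptions. N = 890 × rate; power = Φ(5 / (21.8 × √(2/(N/2))) − 1.960). The fourth column is 801 − N: the observed four-month outcomes discarded if 90% of the 890 (801) supply one.

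| Complete at all time-points | N | Power | Four-month outcomes discarded |
|---|---|---|---|
| 90% | about 801 | 90.1% | 0 |
| 85% | about 756 | 88.4% | about 45 |
| 80% | about 712 | 86.4% | about 89 |
| 70% | about 623 | 81.7% | about 178 |

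If 10% were missing at each of the three questionnaires (again an assumption), completion would lie between 90%, when the same people miss all three, and 100% − 3 × 10% = 70%, when no one misses more than one. That is the range of the table. The figures are before any PP exclusion for treatment or deviation, and ignore any precision gained from the covariates in section 11.4.

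**The case against.** The best defence is that the phrase in 11.3 is a loose rendering of the one used elsewhere. Sections 11, 11.6 and 11.9 all speak of using all available data, and 11.4 plans sensitivity analyses for loss to follow-up and withdrawal. On that view no complete-case filter was meant. This is plausible as to intent, and it is a reason not to claim that a completers' analysis will certainly be run. It does not rescue the text. The ITT sentence limits which participants belong to the population, not which of their data are used, and two analysts following the protocol could analyse different people in the primary test.

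Second, section 11.1 says the PP population will be finalised after a blinded analysis before data-lock. That stands for PP, and gives the sponsor an occasion to correct it. It does not reach the ITT definition, which nothing defers, and section 11.3 itself leaves only the list of major deviations to other documents.

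Three stronger inferences might tempt a reader, and the documents do not support them:

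- That the trial will fall short of 90% power. There is no loss if 90% complete every time-point. Multiplying three independent 10% losses (0.9³ = 72.9%, about 649 participants, 83.2% power) assumes independence, whereas non-response usually clusters in the same people. Adding PP exclusions brings in a separate issue that arises under any PP definition.
- That multiple imputation has nothing left to act on. Section 11.5 is driven largely by resource-use and cost data, which can be missing when every OMAS is present. Only the imputed primary outcome becomes redundant.
- That PP deviations should be limited to the first four months. The contradiction does not require such a rule, and it would sit poorly with PP use in the 12-month economic evaluation.

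**Conclusion.** The point holds as a contradiction that governs who enters the primary test. Section 11.3, as written, gives an analysis set that conflicts with sections 9.11, 11, 11.2, 11.4 and 11.9, and selects on response after the endpoint in both the primary and the supporting analysis. This conclusion comes from the wording alone and needs no assumption about missingness.

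The direction and size of any bias cannot be derived from the protocol. The effect on power is conditional: none at 90% all-time-point completion, modest at 80% to 85%, and down to 81.7% at 70%, with the SD, margin and zero true difference of the plan. The sample size calculation itself is correct. Because the definition is fixed in the protocol and costs nothing to repair, it should be corrected before the analysis populations are finalised.

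**What to change.** In section 11.3, remove the requirement for data at all time-points from both definitions. Define ITT as all randomised participants analysed in their allocated group. Define PP as those who received their allocated treatment and had no major protocol deviation, with the deviations specified elsewhere as now planned. Add one sentence saying that the four-month primary model uses every member of the relevant population with a four-month OMAS or, if a repeated-measures model is adopted, all available post-baseline OMAS values. Carry the same wording into the SHEAP.

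The cost is a wording amendment to the protocol and SHEAP. It needs no extra participants, data collection or change to the sample size.

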11.4. Description of the Statistical Methods

In non-inferiority trials we want to show that the new treatment is not clinically worse than the active control and therefore the interest is one-sided. The new treatment may be better than the control, but it is at least non-inferior to it. We define a non-inferiority margin (Δ_T), which is the maximum difference we are prepared to tolerate in a given direction that the new treatment is not to be considered clinically inferior to the well-established standard treatment. The null hypothesis is therefore that a difference of greater than Δ_T exists in favour of the standard treatment (H₀: $\Delta \le -\Delta_T$) (Δ defined as the difference between treatment and control (T-C)) and the trial is targeted at disproving this in favour of the alternative that the new treatment is non-inferior (H_A : $\Delta \ge -\Delta_T$). This will be assessed by creating a 95% confidence interval which should be entirely above the non-inferiority margin for the new treatment to be declared noninferior. FDA regulations recommend that both a treatment received (per protocol) and intention to treat (ITT) analysis is performed aiming to demonstrate non-inferiority. Use of the ITT approach as in a superiority trial sometimes increases the chance of falsely claiming non-inferiority. Therefore, the primary analysis will be undertaken on the per-protocol population, where only those patients who received their allocated treatment will be analysed and those that do not will be excluded from the analysis. A secondary analysis will be undertaken on the ITT population where all randomised patients will be analysed according to their treatment allocation.

The result of the analysis for the primary endpoint should be one of the following:

- The confidence interval for the difference between the two treatments lies entirely above the noninferiority margin (-ΔT), so that non-inferiority may be concluded with only a small probability of error.
- The confidence interval includes points below the non-inferiority margin, then there is a possibility that the new treatment is inferior to the control and non-inferiority cannot be safely concluded.
- The confidence interval is entirely above zero, indicative of a treatment effect, then superiority of the new treatment can be concluded within a small probability of error.
- The confidence interval is entirely below the non-inferiority margin, indicative of the new treatment being clinically inferior to the control.

As well as assessing if non-inferiority (and superiority) is demonstrated, sensitivity analyses will be undertaken to assess a range of potential biases that could have resulted from loss-to-follow-up, protocol deviations, or withdrawal (including mortality). Numerical and graphical summaries of all data will be

compiled including descriptions of missing data at each level. Estimates of treatment effect will be reported with 95% confidence intervals and a figure showing confidence intervals and margins of non-inferiority will also be presented. The main analytical methods will be generalised linear models and all analyses will adjust for important baseline covariates to maximise precision.

The OMAS score ²¹ at four months is the primary outcome in this study and will be compared between treatment groups as the dependent variable in a mixed-effects linear regression model for the primary analysis with adjustments for stratification factors and baseline (pre-injury) OMAS score. ²¹ A random effect will be included to account for any heterogeneity in the response due to recruitment centre. Fixed effects will be included to adjust for participant age and gender and fracture stability. The treatment difference will be based on the estimate of adjusted means and 95% confidence intervals. A fully adjusted analysis will also be undertaken adjusting for additional important prognostic variables using the same methods and an unadjusted analysis will also be undertaken using Analysis of Covariance adjusting for baseline OMAS scores only. ²¹ Supplementary analyses will also be conducted for the OMAS score ²¹ using the area under the curve (AUC) summary statistics. ³⁵

Where severe departure from normality is identified, the first approach will be data transformation. If the data cannot be transformed to normality then the Mann-Whitney U test will be used (in this case, no further adjustments will be made). The primary focus will be the comparison of the two treatment groups of participants, and this will be reflected in the analysis which will be reported together with appropriate diagnostic plots that check the underlying model assumptions. The adjusted analysis using the perprotocol population will be considered the primary analysis to determine non-inferiority and superiority (if shown to be non-inferior) with the additional analyses, including using the intention-to-treat population, providing supporting evidence. Secondary clinical outcomes will be similarly analysed using mixed effects regression, using logistic regression for binary data and linear regression for continuous data.

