9.4. Randomisation

Once informed consent has been given, the participant will be randomised by the local research team using a web-based service.

Allocations will be implemented as close as possible to the time of surgical decision-making once the participant has consented, whether this be in outpatient clinics or daily trauma meetings. Such a design most faithfully replicates real clinical practice so that the results of the trial will be as generalisable as possible to the wider NHS. This trial will test the two interventions as treatment pathways and hence be as pragmatic as possible.

The randomisation will be on a 1:1 basis, using a validated computer randomisation program managed through a secure (encrypted) web-based service by the Oxford Clinical Trials Research Unit, with a minimisation algorithm to ensure balanced allocation across the treatment groups, stratified by centre and fracture stability (defined as the presence of a posterior malleolus fracture). The minimisation algorithm will include a probabilistic element and a small number of participants randomised by simple randomisation at the start of the trial to seed the algorithm in order to ensure the unpredictability of treatment allocation.²⁷

Stratification by centre will help to ensure that any centre-effect will be equally distributed in the trial arms. While it is possible that the surgeons at one centre may be more expert in one or the other treatment than those at another centre, all of the recruiting hospitals have been/will be chosen on the basis that both techniques are currently routinely available at the centre i.e. theatre staff and surgeons will already be equally familiar with both forms of intervention. Similar to the findings from other trauma trials, we anticipate that each individual surgeon will only treat 2-3 participants enrolled in the trial, greatly reducing the risk of a surgeon-specific effect upon the outcome in any one centre. We will also incorporate centre as a random effect in the mixed effect primary analysis which takes into account any heterogeneity between centres. Stratification by fracture stability, specifically the presence or absence of a fracture of the posterior malleolus, will ensure that this important confounder is balanced between groups.

On randomisation of a participant the central trial office, main site contact and local study team will be notified. This will take place via an automated email as part of the randomisation process.

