9.6.2. Non-surgical treatment

Participants will undergo close contact casting (CCC). Close contact casting is now an established intervention and is recommended as the primary treatment for adults over 60 years of age with unstable fractures in the current NICE guidance.⁶

In consultation with patients and patient representatives during the development of the trial protocol, and in common with the established practice for older adults based upon the non-surgical intervention tested in the AIM trial,³ all initial manipulations and applications of CCC will take place under anaesthesia.

The method of closed fracture manipulative reduction of deformity under image intensifier guidance will be left to individual surgeons and this falls within the common contemporary skills set of trauma and orthopaedic surgeons. The anaesthetic technique will be left to the discretion of the treating anaesthetist.

The CCC will be applied to the ankle once, in the opinion of the treating surgeon, the fracture has been adequately reduced. There will be standardisation of the casting materials, cast design and application, and moulding technique, as per the AIM trial training package.³ This technique will be revisited with clinical teams at each site with the FAME training team. In the event that an acceptable closed reduction cannot be achieved then the operating surgeon will proceed to open reduction and internal fixation (ORIF) if this is clinically appropriate. Conversion to ORIF in these circumstances, where an acceptable reduction cannot be achieved or maintained intraoperatively, will not constitute a protocol violation. Details of the reasons and the surgical technique used will be recorded.

Participants will be non-weight bearing for the duration of the CCC treatment.

The clinical follow-up schedule in the early phase will be left to the discretion of the treating surgeon. It is anticipated that some participants will require repeat applications of the CCC as the swelling around the injured ankle reduces. Subsequent applications of the CCC can be performed outside of an operating theatre, for example in plaster rooms. Advice regarding the frequency of clinical monitoring will be provided in the training sessions and rehabilitation booklet. After reapplications of the CCC repeat radiographs will be performed to confirm the reduction has been maintained.

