11.1. Statistical & Health Economics Analysis Plan

A statistical and health economic analysis plan (SHEAP) with full details of all analyses will be drafted early in the trial and finalised prior to primary outcome analysis. The SHEAP will be reviewed and will receive input from the Trial Steering Committee (TSC) and the Data Safety and Monitoring Committee (DSMC). Any changes or deviations from the original SHEAP will be described and justified in the protocol, an updated SHEAP, final report and publications as applicable, depending on the timing of the changes. Interim analyses of efficacy outcomes are not planned and will be performed only where requested by the DSMC. Following a blinded analysis of the data, undertaken prior to the final data-lock, the per-protocol population will be finalised and the SHEAP updated. It is anticipated that all analysis will be undertaken using Stata (StataCorp LP, www.stata.com) or other well-validated statistical packages.

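### The protocol permits intraoperative conversion from casting to ORIF, but the literal per-protocol definition drops those participants from the decisive analysis, in one arm only

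*Protocol*

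**What the plan says.** Section 9.6.2 names close contact casting (CCC) as the treatment for the non-surgical arm and provides for ORIF, if clinically appropriate, when closed reduction fails in theatre. It then states: "Conversion to ORIF in these circumstances, where an acceptable reduction cannot be achieved or maintained intraoperatively, will not constitute a protocol violation". Section 9.4 says: "This trial will test the two interventions as treatment pathways and hence be as pragmatic as possible". Section 10.3 lists failed closed reduction among the events related to CCC only.

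Section 11.3 defines the per-protocol (PP) population by two separate conditions; it "will include all patients who received their allocated treatment and did not have any major protocol deviations". Section 11.4 repeats the first condition for the primary analysis: "only those patients who received their allocated treatment will be analysed and those that do not will be excluded from the analysis". The adjusted PP analysis "will be considered the primary analysis to determine non-inferiority and superiority", "with the additional analyses, including using the intention-to-treat population, providing supporting evidence".

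The list of major deviations is left to the Data Management Plan and the SHEAP. On timing, section 11.1 says: "Following a blinded analysis of the data, undertaken prior to the final data-lock, the per-protocol population will be finalised and the SHEAP updated". No section says whether an intraoperative converter has received the allocated treatment.

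**The concern.** A cast-arm participant whose reduction fails in theatre and who then has ORIF has followed the protocol. On the plain wording of 11.3 and 11.4 that participant has still not received CCC, and so leaves the analysis that decides the trial.

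Two features make this more than untidy drafting. First, the exclusion depends on an event after randomisation that can occur in one arm only. Fractures in the surgical arm that would also have resisted closed reduction cannot be identified, so they stay in. Adjusting for posterior malleolus fracture, age, gender and baseline OMAS does not restore a comparison broken by an intraoperative event. Second, ITT has no vote. If PP clears the margin and ITT does not, the stated rule still declares non-inferiority.

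Leaving major deviations to the SHEAP does not settle the matter. Receipt of the allocated treatment is its own condition, already fixed in the protocol; ruling that conversion is not a major deviation would leave that condition unmet.

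**Working it through.** **Inputs from the protocol (sections 9.4 and 11.2).** Margin 5 OMAS points, SD 21.8, one-sided 2.5%, power 90%, 1:1 allocation, 800 evaluable, 10% loss to follow-up, 890 randomised.

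**Reproducing the design.** n per arm = 2 × 21.8² × (1.960 + 1.282)² / 5² ≈ 400, so 800 in total. Power with 400 per arm: SE = 21.8 × √(2/400) = 1.541; Φ(5/1.541 − 1.960) = 90.0%. Then 800/0.9 = 889, or 890 with equal arms. The stated sample size is right, but it makes no allowance for PP exclusions.

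**Assumptions (not in the protocol).** p = share of the CCC arm converting intraoperatively. d = mean OMAS of those kept in cast minus mean OMAS of converters. All of d is taken as unexplained by the model covariates, and the SD is kept at 21.8.

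**Shift.** The full CCC mean is the kept-in-cast mean minus p × d. Excluding converters therefore moves the treatment difference by +p × d.

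**Type I error.** SE = 21.8 × √(1/400 + 1/(400(1 − p))). At a true pathway difference of −5, the chance of declaring non-inferiority is Φ(p × d/SE − 1.960).

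Worked case, p = 10%, d = 10: SE = 21.8 × √(1/400 + 1/360) = 1.584; shift = +1.0 point, which is 1.0/5 = 20% of the margin; Φ(1.0/1.584 − 1.960) = 9.2%.

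One-sided type I error (nominal 2.5%), with the shift in points in brackets:

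| p | d = −5 | d = 0 | d = 5 | d = 10 | d = 15 |
|---|---|---|---|---|---|
| 5% | 1.7% (−0.25) | 2.5% (0) | 3.6% (+0.25) | 5.1% (+0.50) | 7.0% (+0.75) |
| 10% | 1.1% (−0.50) | 2.5% (0) | 5.0% (+0.50) | 9.2% (+1.0) | 15.6% (+1.5) |
| 20% | 0.5% (−1.0) | 2.5% (0) | 8.9% (+1.0) | 23.1% (+2.0) | 45.0% (+3.0) |

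**Power if converters are excluded, true difference zero and d = 0.** Φ(5/SE − 1.960) = 89.3% at p = 5% (SE 1.562), 88.4% at p = 10% (SE 1.584) and 86.4% at p = 20% (SE 1.635), against 90.0% as planned.

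**Which analysis is the lenient one?** Suppose casting costs 5 points in those held in cast, converters do as well as they would have done with primary surgery, and their fractures carry a prognostic shortfall of s points. PP then estimates −5 + p × s and ITT estimates −5(1 − p). In this setting d = s − 5. At p = 10%:

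- s = 0: PP −5.0, ITT −4.5 (PP stricter)
- s = 5: both −4.5
- s = 10: PP −4.0, ITT −4.5 (PP more lenient)

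Either analysis can therefore be the one that lets casting through too easily.

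**The case against.** The best defence is that the text can be read the other way. Conversion is described inside the section on the non-surgical treatment and is declared not to be a violation, so a trial team could reasonably treat converters as having received their allocation. That is a fair reading. It makes this an inconsistency to be reconciled, not a demonstrated exclusion. A reader might infer that the protocol calls conversion part of the allocated pathway, or that it expressly removes converters. It does neither: the pathway sentence in 9.4 is general, and removal follows only from the literal wording of 11.3 and 11.4. The statement in 9.6.2 also covers intraoperative failure alone; that section does not address loss of reduction after theatre.

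A second defence is that converters receive the comparator. Keeping them under CCC can dilute a real casting deficit, and fear that ITT may falsely favour non-inferiority is the protocol's own reason for preferring PP. This also stands, and the last comparison in the working shows it.

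Third, the PP rule applies to both arms, so it would be wrong to say that casting successes are compared with every surgical participant. ITT is reported, and sensitivity analyses for protocol deviations are planned. These show a discrepancy but do not change the decision rule.

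Finally, a reader might infer that the blinded review is worthless because a conversion identifies the arm. It does identify those individuals' arm, but a rule can still be set without sight of outcomes by arm. This is a reason to fix the rule early, not a separate fault.

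**Conclusion.** The inconsistency between 9.6.2 and 11.3/11.4 is real and bears on the analysis that decides the trial. Its effect on the estimate is p × d. For p of 5–20% and d of 5–15 points that is 0.25–3.0 points towards casting against a 5-point margin, with type I error of 3.6–45%; the upper figure is the extreme corner of the assumed range.

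It is tempting to conclude that the plan biases the trial towards non-inferiority. The protocol does not support that as a general statement, because it gives neither the conversion rate nor how converters fare. A worse outcome in converters is plausible but not shown. If they do the same, only power is lost (90% falls to 86–89%); if they do 5 points better, the error falls to 0.5–1.7%. What holds without any assumption is that membership of the decisive set is unsettled for protocol-compliant participants, and that ITT cannot overturn a PP pass. This should be fixed; confidence is moderate.

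**What to change.** 1. Reconcile 11.3 and 11.4 with 9.6.2 by stating, before any data review, whether an intraoperative converter counts as having received the allocated treatment for the PP set. Retaining converters under CCC fits the pathway question in 9.4. This concerns analysis sets only, not the clinical decision to convert.
2. Declare non-inferiority only if the lower 95% bound exceeds −5 in both the ITT and the PP analyses. Section 11.4 already cites regulatory advice that both be performed, and requiring both guards against error in either direction.
3. Report the primary comparison with converters in and with converters out.

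The cost is wording in the protocol and SHEAP, plus a slightly stricter test: joint power cannot exceed the lower of the two, for example 88.4% at p = 10% with converters out, d = 0 and no true difference. Retaining converters may dilute a true casting deficit and brings PP closer to ITT, so the second requirement then adds less; the converters-out result would show any such dilution.
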